10.3.1 Definition of AE

AE definition

- An AE is any untoward medical occurrence in a clinical study participant, temporally associated with the use of study intervention, whether or not considered related to the study intervention.
- NOTE: An AE can therefore be any unfavorable and unintended sign (including an abnormal laboratory finding), symptom, or disease (new or exacerbated) temporally associated with the use of a study intervention.
- NOTE: For purposes of AE definition, study intervention (also referred to as Sponsor's product) includes any pharmaceutical product, biological product, vaccine, diagnostic agent, or protocol specified procedure whether investigational or marketed (including placebo, active comparator product, or run-in intervention), manufactured by, licensed by, provided by, or distributed by the Sponsor for human use in this study.

Events meeting the AE definition

- Any abnormal laboratory test results (hematology, clinical chemistry, or urinalysis) or other safety assessments (eg, ECG, radiological scans, vital signs measurements), including those that worsen from baseline, or are considered clinically significant in the medical and scientific judgment of the investigator.
- Exacerbation of a chronic or intermittent pre-existing condition including either an increase in frequency and/or intensity of the condition.
- New conditions detected or diagnosed after study intervention administration even though it may have been present before the start of the study.
- Signs, symptoms, or the clinical sequelae of a suspected drug-drug interaction.
- Signs, symptoms, or the clinical sequelae of a suspected overdose of either study intervention or a concomitant medication.
- For all reports of overdose (whether accidental or intentional) with an associated AE, the AE term should reflect the clinical symptoms or abnormal test result. An overdose without any associated clinical symptoms or abnormal laboratory results is reported using the terminology "accidental or intentional overdose without adverse effect."

Events NOT meeting the AE definition

- Medical or surgical procedure (eg, endoscopy, appendectomy): the condition that leads to the procedure is the AE.
- Situations in which an untoward medical occurrence did not occur (social and/or convenience admission to a hospital).
- Anticipated day-to-day fluctuations of pre-existing disease(s) or condition(s) present or detected at the start of the study that do not worsen.

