Section 3.6.1 Statistical Methods for Immunogenicity Analyses	Added a paragraph to provide Reverse Cumulative Distribution Curves for IgG concentrations and OPA Titers at 30 Days Postdose 3 and 30 Days Postdose 4.	Added to provide additional statistical analysis details/data derivations.
Section 3.6.2 Statistical Methods for Safety Analyses	Added a paragraph to explain the rationale for not including vaccination-site AEs in the summary tables.	Added to provide additional statistical analysis details/data derivations.
Section 3.6.2 Statistical Methods for Safety Analyses	Added a paragraph to explain the rationale for not including laboratory AEs in the summary tables.	Added to provide additional statistical analysis details/data derivations.
Section 3.6.2 Statistical Methods for Safety Analyses	Added a paragraph to describe an additional supportive analysis of the proportion of participants with solicited complaints using the data collected directly from participants via the VRC.	Added to provide additional statistical analysis details/data derivations.
Section 3.6.3 Summaries of Demographic and Baseline Characteristics	Added a sentence to specify the age variable used for the analyses.	Added to provide additional statistical analysis details/data derivations.
Section 3.10 Subgroup Analyses	Added details of subgroup analyses.	Added to provide additional statistical analysis details/data derivations.
Throughout	Corrected minor typographical and grammatical errors.	Revisions made for accuracy.

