3. ANALYTICAL AND METHODOLOGICAL DETAILS

3.1 Statistical Analysis Plan Summary

Key elements of the statistical analysis plan are summarized below; the comprehensive plan is provided in Sections 3.2 through 3.12.

Study Design Overview	A Phase 3, Multicenter, Randomized, Double-blind, Active Comparator-controlled Study to Evaluate the Safety and Tolerability of V114 in Healthy Infants (PNEU-LINK)
Intervention Assignment	Approximately 2400 healthy infants approximately 2 months of age will be enrolled. 
 • Full-term infants (gestational age ≥ 37 weeks) will be randomly assigned in a 5:1 ratio to a complete dosing schedule of V114 or Prevnar 13™. • Premature infants (gestational age < 37 weeks) will be randomly assigned in a 1:1 ratio to a complete dosing schedule of V114 or Prevnar 13™
Analysis Populations	Safety: All Participants as Treated (APaT) Immunogenicity: Per-Protocol (PP) and Full Analysis Set (FAS) population for the Premature Infant Immunogenicity Substudy
Primary Endpoint(s)	
 • Proportion of participants with solicited injection-site AEs (swelling, redness/erythema, tenderness/pain, and hard lump/induration) from Day 1 through Day 14 following any vaccination with V114 or Prevnar 13™ • Proportion of participants with solicited systemic AEs (irritability, drowsiness/somnolence, appetite lost/decreased appetite, and hives or welts/urticaria) from Day 1 through Day 14 following any vaccination with V114 or Prevnar 13™ • Proportion of participants with vaccine-related SAEs from Day 1 through completion of study participation
Key Secondary Endpoint(s)	Premature Infant Immunogenicity Substudy only: 
 • Anti-pneumococcal polysaccharide (PnPs) serotype-specific Immunoglobulin G (IgG) Geometric Mean Concentrations (GMCs) for the 15 serotypes contained in V114 at 30 days PD3, prior to Dose 4 and at 30 days PD4 • Anti-PnPs serotype-specific IgG response rates (proportion of participants meeting serotype-specific IgG threshold value of ≥ 0.35 $\mu\text{g/mL}$) for the 15 serotypes contained in V114 at 30 days PD3
Statistical Methods for Key Immunogenicity Analyses	Immunogenicity analyses will be conducted for each of the 15 pneumococcal serotypes contained in V114 separately. To address the immunogenicity objectives, evaluation of the anti-PnPs serotype-specific IgG GMCs and response rates will be summarized descriptively.

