3.4.2 Safety Endpoints

A description of safety measures is contained in Sections 8.3 and 8.4 of the protocol. The analysis of safety results is described in Section 3.6.2.

Safety and tolerability will be assessed by clinical review of all relevant parameters including adverse events and postvaccination temperature measurements following any vaccination with V114 or Prevnar 13™.

The safety analysis endpoints include:

- Proportion of participants with solicited injection-site AEs (swelling, redness/erythema, tenderness/pain, and hard lump/induration) from Day 1 through Day 14 following any vaccination with V114 or Prevnar 13™
- Proportion of participants with solicited systemic AEs (irritability, drowsiness/somnolence, hives or welts/urticaria, and appetite loss/decreased appetite) from Day 1 through Day 14 following any vaccination with V114 or Prevnar 13™
- Proportions of participants with the broad AE categories consisting of any AE, a vaccine-related AE, an SAE, an AE which is both vaccine-related and serious, and discontinuation due to an AE, and the proportion of participants who died
- Participants body temperature measured Day 1 (day of vaccination) through Day 7 following any vaccination with V114 or Prevnar 13™

The timeframe associated with the reporting of AEs is consistent with the collection. Nonserious adverse events (NSAEs) are reported from Day 1 through Day 14 following each vaccination. SAEs are reported from Day 1 through completion of study participation.

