Membership in Tier 2 requires that at least 1% of the participants in either treatment group exhibit the event. The threshold of at least 1% was chosen because when less than 1% of participants report AEs in both groups with more events in the V114 group, the 95% CI for the between-group difference in percent incidence will always include zero. Note that when less than 1% of participants report AEs in both groups but with more events in the Prevnar 13™ group or equal in both groups, the 95% CI for the between-group difference may exclude zero. However, the clinical significance of these differences is unknown given the small number of participants who report AEs in this situation (1% of the participants in either treatment group) and; therefore, these AEs will be categorized as Tier 3 events. Because many 95% CIs for Tier 2 events may be provided without adjustment for multiplicity, the CIs should be regarded as a helpful descriptive measure to be used in review, not a formal method for assessing the statistical significance of the between-group differences in AEs and safety parameters that meet predefined limits of change.

In addition to individual events that occur in at least 1% of participants in any treatment group, the broad AE categories consisting of the proportion of participants with any AE, a vaccine-related AE, an SAE, a vaccine-related SAE, discontinuation due to an AE, and the proportion of participants who died will be considered Tier 2 endpoints.

Tier 3 Events

Safety endpoints that are not Tier 1 or 2 events are considered Tier 3 events. Only point estimates by treatment group are provided for Tier 3 safety parameters.

Table 3 Analysis Strategy for Safety Parameters

Safety Tier	Safety Endpoint [†]	p-Value	95% CI for Between-Group Comparison	Descriptive Statistics
Tier 1	Injection-site redness/erythema (Days 1 to 14)	X	X	X
	Injection-site swelling (Days 1 to 14)	X	X	X
	Injection-site tenderness/pain (Days 1 to 14)	X	X	X
	Injection-site hard lump/induration (Days 1 to 14)	X	X	X
	Irritability (Days 1 to 14)	X	X	X
	Drowsiness/somnolence (Days 1 to 14)	X	X	X
	Hives or welts/urticaria (Days 1 to 14)	X	X	X
	Appetite loss/decreased appetite (Days 1 to 14)	X	X	X
Tier 2	Any AE [†]		X	X
	Any Vaccine-Related AE [†]		X	X
	Any SAE [†]		X	X
	Any Vaccine-Related SAE [†]		X	X
	Discontinuation due to AE [†]		X	X
	Death [†]		X	X
	Maximum temperature measurements meeting the Brighton Collaboration cut points (Days 1 to 7)		X	X

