Tier 3	Specific AEs by SOC and PT [‡] (incidence $\geq 1\%$ of participants in one of the vaccination groups)		X	X
	Specific AEs by SOC and PT [‡] (incidence $< 1\%$ of participants in all of the vaccination groups)			X

[†] These endpoints are broad adverse event categories. For example, descriptive statistics for the safety endpoint of “Any AE” will provide the number and percentage of participants with at least one AE.
[‡] Includes only those endpoints not pre-specified as Tier 1 or not already pre-specified as Tier 2 endpoints.
 AE = adverse event; CI = confidence interval; PT = preferred term; SAE = serious adverse event;
 SOC = system organ class; X = results will be provided

Laboratory AEs will not be reported in summary tables as laboratory testing is not performed as part of the study and thus such AEs would only be reported spontaneously. A listing of laboratory AEs will be provided.

A supportive analysis comparing the proportion of participants reporting each of the solicited complaints on the VRC will be conducted in support of the primary safety analyses that are based on solicited AEs. This supportive analysis will use the methodology specified in Table 3 for solicited AEs. The analysis will be conducted on the subset of the APaT population who entered solicited complaints data on the VRC.

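### The sSAP keeps every laboratory AE out of summary tables, which conflicts with a primary vaccine-related SAE endpoint and broad AE categories that have no laboratory exclusion

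*Combined protocol and SAP*

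**What the plan says.** The rule is in sSAP Section 3.6.2, after Table 3: "Laboratory AEs will not be reported in summary tables as laboratory testing is not performed as part of the study". The reason continues that such events would therefore come to light only through spontaneous reports. The next sentence gives the alternative: "A listing of laboratory AEs will be provided". The sSAP change log (Section 2.1) records this as new relative to the protocol SAP: "Added a paragraph to explain the rationale for not including laboratory AEs in the summary tables". Neither place makes an exception, and protocol Section 9.6.2 has no such rule.

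The endpoints are defined without reference to laboratory origin. The third primary endpoint in sSAP Section 3.1 is "Proportion of participants with vaccine-related SAEs from Day 1 through completion of study participation". Section 3.4.2 lists "Proportions of participants with the broad AE categories consisting of any AE, a vaccine-related AE, an SAE, an AE which is both vaccine-related and serious", then discontinuation due to an AE and death. Section 3.6.2 repeats that "an SAE, a vaccine-related SAE, discontinuation due to an AE, and the proportion of participants who died will be considered Tier 2 endpoints". The Table 3 footnote says that the statistics for the any-AE row "will provide the number and percentage of participants with at least one AE".

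Protocol Section 10.3.1 opens its list of qualifying AEs with "Any abnormal laboratory test results (hematology, clinical chemistry, or urinalysis", so a laboratory finding can be an AE. If it also meets a seriousness criterion in Section 10.3.2, it is an SAE.

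**The concern.** The primary SAE proportion and the broad categories are themselves summary-table results. A programmer who follows the laboratory sentence would remove laboratory AEs before counting; one who follows the endpoint definitions would not. The plan therefore allows two numerators for a primary endpoint, and for the SAE, discontinuation and death rows.

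The stated reason does not cover the serious cases. The absence of protocol laboratory testing is a fair argument against tabulating rates of nonserious laboratory findings, which depend on whether someone happened to order a test. It does not explain omitting an SAE, because protocol Section 8.4.1 and sSAP Section 3.4.2 require SAEs to be reported through the end of participation, whatever prompted their detection.

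Safety is the purpose of this trial. Where counts are very low, one event more or less is visible in the result.

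**Working it through.** **1. Texts side by side**

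| Place | What is counted or shown | Laboratory exclusion? |
|---|---|---|
| sSAP 3.1, third primary endpoint | Participants with a vaccine-related SAE | None |
| sSAP 3.4.2 and Tier 2 text in 3.6.2 | Any AE, related AE, SAE, related SAE, discontinuation, death | None |
| sSAP Table 3 footnote | Participants with one or more AEs | None |
| sSAP 3.6.2, after Table 3 | Laboratory AEs: listing only | All, no exception |
| Protocol 10.3.1 | Laboratory abnormalities can be AEs | Not applicable |

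The fourth row cannot be applied literally together with the first three if any laboratory-coded event qualifies for them.

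**2. The plan's own figures (sSAP 3.9.2, n = 2,000 on V114, SAEs of any kind)**

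- Chance of at least one event: 1 − (1 − p)^2000. With p = 1/1243 this is 0.8000; with p = 1/2886 it is 0.5000.
- Exact one-sided 97.5% upper bound for 0/2000: 1 − 0.025^(1/2000) = 0.1843%, or 1 in 542.7.

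All three agree with the stated 80%, 50% and 0.18% (1 in 543).

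**3. Effect of one omitted event (hypothetical count)**

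- Counted, 1/2000 = 0.05%. The Clopper-Pearson upper limit solves (1 − p)^2000 + 2000p(1 − p)^1999 = 0.025, giving p = 0.2783%, or 1 in 359. The lower limit is 1 − 0.975^(1/2000) = 0.0013%.
- Omitted, the table shows 0/2000 with upper limit 0.1843%.

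**4. The same case on the output that Table 3 plans**

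For vaccine-related SAEs, Table 3 provides a Miettinen-Nurminen 95% CI for the difference (V114 minus Prevnar 13, 2,000 versus 400).

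- One V114 event counted, none on Prevnar 13: +0.05 percentage points (−0.90 to +0.28).
- That event omitted: 0.00 (−0.95 to +0.19).

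**5. Sensitivity to an assumed share**

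The documents give no proportion of SAEs that would be laboratory-coded. Let f be the share of participants with an SAE who have only such an event. The chance of tabulating at least one SAE is then 1 − (1 − (1 − f)/1243)^2000. This is 0.7935 at f = 2% and 0.7241 at f = 20%, against 0.8000. With 2886 in place of 1243 it is 0.4930 and 0.4256, against 0.5000. The values of f are assumptions chosen to show a range.

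**The case against.** The strongest reply is that the sentence governs what tables show and does not amend an endpoint. The sSAP introduction limits its modifications to ones that are not principal in nature, and the change log classes this paragraph as added analysis detail. The sponsor may have had only the term-level tables in mind. That stands against a reading that some may be tempted to adopt: that the plan redefines or shrinks the primary endpoint. The documents do not support that. They support only an unresolved conflict, because nothing limits the sentence to term-level tables.

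Second, laboratory-coded SAEs should be uncommon. Protocol Section 10.3.4 has the investigator seek a diagnosis and record it in place of individual signs, and Section 10.3.2 names blood dyscrasias as a possible serious event. A child admitted with a low platelet or neutrophil count might therefore be recorded under a clinical diagnosis. As the sSAP does not define a laboratory AE, one cannot say that such a case would be excluded. This limits likelihood but does not supply the missing exception.

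Third, a reader might infer that the rationale applies equally to all unsolicited AEs and SAEs. It does not. Unsolicited AEs are sought through the eVRC (protocol Section 8.3.3), the Day 15 call (8.1.10) and open-ended questions (8.4.2), and SAEs at the six-month call (8.1.11). Listing nonserious laboratory findings separately is defensible. The gap concerns serious events and discontinuations.

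Fourth, the 0.18% in sSAP Section 3.9.2 is a planning figure for SAEs of any kind. No single-arm exact bound for vaccine-related SAEs is a planned output, so the rule should not be said to make a reported bound too low. Nor should much be made of a scenario with one related SAE per group, in which omitting only the V114 event moves the interval from (−1.35, +0.09) to (−1.40, −0.04) percentage points. That result comes from choosing which arm loses its event.

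Finally, comparisons are descriptive with no hypothesis test, the events remain in a listing and in SAE reporting to the sponsor, and a participant with another event qualifying for the same category is still counted. All of this holds and keeps the point modest.

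**Conclusion.** The point holds as a conflict between a stated reporting rule and the endpoint definitions. Taken literally, the rule would leave a laboratory-coded SAE, vaccine-related SAE, fatal event or AE leading to discontinuation out of the matching counts, and no text in either document exempts such events. Whether the sponsor intended this cannot be settled from the documents.

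The expected effect is small and its frequency unknown. The illustration (upper limit 0.28% with one event counted, 0.18% with it omitted) assumes 2,000 evaluable V114 participants and a single vaccine-related SAE that is laboratory-coded in a participant with no other qualifying event. The sample-size figures are unaffected.

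**What to change.** Amend the paragraph in sSAP Section 3.6.2 as follows:

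- Confine the exclusion to nonserious laboratory AEs that do not lead to discontinuation, and to the tables by SOC and PT.
- State that laboratory AEs that are serious, both serious and vaccine-related, fatal, or lead to discontinuation count in the matching broad categories of Table 3, and that those both serious and vaccine-related count in the primary vaccine-related SAE endpoint.
- State whether nonserious laboratory AEs count in the any-AE and vaccine-related-AE rows.
- Define a laboratory AE, for example by reference to the coding terms used.
- Keep the listing.

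If the tables have already been produced, the report should say for each category whether any laboratory AE was left out. The cost is a few sentences and a few extra low-frequency counts. No additional data are needed.

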3.6.3 Demographic and Baseline Characteristics

The comparability of the vaccination groups for each relevant demographic and baseline characteristic will be assessed by the use of summary tables. No statistical hypothesis tests will be performed on these characteristics. The number and percentage of participants screened and randomized and the primary reasons for screening failure and discontinuation will be displayed. Demographic variables (e.g., age, race, gender, and gestational age), baseline characteristics, prior and concomitant vaccinations and therapies will be summarized by vaccination group either by descriptive statistics or categorical tables.

Demographic variables and baseline characteristics will also be summarized for the Premature Infant Immunogenicity Substudy.

Calculated age based on the difference in months between the birthdate and randomization date will be used for summaries of age.

3.7 INTERIM ANALYSES

A periodic review of safety and tolerability data across the V114 Phase 3 pediatric program will be conducted by an independent, unblinded, external DMC. A description of the structure, function, and guidelines for decision-making by the DMC, along with the timing and content of the safety reviews will be outlined in the DMC Charter. Information regarding the composition of the DMC is provided in Appendix 1. There are no plans to conduct an interim analysis of unblinded immunogenicity data in this study. However, unblinded immunogenicity data from this study and other ongoing V114 clinical studies will be made available to the DMC upon request to enable a benefit-risk assessment.

Study enrollment is likely to be ongoing at the time of any interim analyses. Blinding to intervention assignment will be maintained at all investigational sites. The results of interim analyses will not be shared with the investigators prior to the completion of the study. Participant-level unblinding will be restricted to an external unblinded statistician performing interim analyses.

The DMC will serve as the primary reviewer of the results of the safety interim analyses and will make recommendations for discontinuation of the study or protocol modifications to an executive committee of the Sponsor (see Appendix 1 for details on the Committees Structure for this study). If the DMC recommends modifications to the design of the protocol or discontinuation of the study, this Executive Oversight Committee (EOC) of the Sponsor (and potentially other limited Sponsor personnel) may be unblinded to results at the intervention level in order to act on these recommendations. The extent to which individuals are unblinded with respect to results of interim analyses will be documented by the external unblinded statistician. Additional logistical details will be provided in the DMC Charter.

Intervention-level results from the safety interim analysis will be provided by the external unblinded statistician to the DMC. Prior to final study unblinding, the external unblinded statistician will not be involved in any discussions regarding modifications to the protocol, statistical methods, identification of protocol deviations, or data validation efforts after the interim analyses.

3.8 MULTIPLICITY

No multiplicity adjustment is planned as there is no formal hypothesis testing.

